#### **8.4.1 Specific criteria for withdrawal (if applicable)**

N/A

### **8.5 Replacement of individual subjects after withdrawal**

With respect to patients applicable for this study willing to participate, and who have signed informed consent (paragraph 11.2): before randomization any patient will be replaced if the patient withdraws for any reason. These patients are not included in the statistical analysis. After the randomization, patients withdrawing for any reason will not be substituted by additional patients and these patients are analyzed by intention to treat.

### **8.6 Follow-up of subjects withdrawn from treatment**

Patients who withdraw after randomization will not be requested to participate for follow-up questionnaires. Patients are asked if it is allowed to consult their medical chart for treatment characteristics and survival length.

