### 8.3 Study procedures

Procedures which are part of the standard medical treatment are summarized in paragraphs 8.3.1-8.3.9. Measurements which are specifically measured for this study are listed in paragraph 8.3.10. A study flow chart is shown in figure 1. A treatment summary table, including an overview of what is and is not part of standard of care, is shown in table 1.

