**Figure 1: Study flow chart**

**Table 1 Study parameter summary table**

	Baseline	End of RT	Months post (f)SRT								
			3M	6M	9M	12M	15M	18M	21M	24M	
Standard clinical care:											
Clinical characteristics: year of birth, gender, primary tumor type, presence of extracranial visceral metastases, primary tumor control, date diagnosis primary tumor, type of systemic therapy	X										
Coded data (see paragraph 12.1): patient number in electronic patient dossier											
Planning MRI & CT: number of brain metastases, total volume of brain metastases, volume of largest brain metastases	X										
Treatment characteristics: GTV largest metastasis, PTV largest metastasis, total volume GTV of all metastases, and total volume PTV of all metastases. Maximum dose in the PTV in anymetastasis. Maximum dose brain stem, chiasm, and optic nerves		X									
Physical examination	X										
WHO-PS and/or KPS	X										
Standard follow-up:											
Follow-up MRI: adverse local event (either radionecrosis or local failure according to RANO), distant brain recurrences			X	X	X	X	X	X	X	X	
Toxicity (CTCAE v5.0)			X	X	X	X	X	X	X	X	
Not part of standard follow-up:											
HRQoL (EORTC QLQ-C30, QLQ-BN20)	X		X	X		X		X		X	
IADL ( EQ-5D 5L)	X		X	X		X		X		X	
Other follow-up:											
Use of dexamethasone or bevacizumab	X		X	X	X	X	X	X	X	X	
Use of AED	X		X	X	X	X	X	X	X	X	
Salvage treatment, type of salvage treatment, date of salvage treatment						X					X
Alive/dead			X	X	X	X	X	X	X	X	
Symptomatic radionecrosis or local failure			X	X	X	X	X	X	X	X	

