### **8.3.9 MR imaging after SRT**

Tumor response evaluation as well as presence of distant brain recurrences are monitored every three months after SRT on contrast-enhanced (single - triple dose Gd is allowed) T1-sequences, maximum slice thickness 3 mm, field strength (1.0-3.0 Tesla with a 3D-distortion correction protocol including perfusion MR).

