## **8.4 Withdrawal of individual subjects**

Subjects can leave the study at any time for any reason if they wish to do so without any consequences. The investigator can decide to withdraw a subject from the study for urgent medical reasons.

If a subject becomes incapacitated during the study period, and if it will no longer be possible to make MRI scans, to send questionnaires, to evaluate toxicity, etc. In such a case, the same guidelines are followed as described for subjects who withdraw from the study for any reason (see 8.5 and 8.6).

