### 10.2 Secondary study parameter(s)

Secondary study parameters (as listed in paragraph 8.1.2, including facultative endpoints such as HRQoL and neurocognition) will be presented per cohort. Due to the presence of repeated measurements mixed modelling will be used to analyze use of anti-epileptica, dexamethasone and bevacizumab, IADL and to investigate the effect of fSRT on quality of life.

Overall survival (from date of first radiotherapy until death) will be estimated by using Kaplan-Meier methodology. To assess whether there is difference between survival in the groups, the Log-rank test will be used. To investigate the effect of prognostic factors on survival, a Cox regression model will be used. To estimate the cumulative incidence of adverse local events (ALE), a competing risk model with death as a competing risk will be estimated. Fine and Gray's test will be employed to assess the difference between cumulative incidence in the two cohorts. Cause specific hazard Cox model will be employed to investigate the effect of prognostic factors on the cumulative incidence of ALE.

Care will be taken to minimize missing data and to continue to follow up those who withdraw from the study. To account for non-compliance and protocol deviation the analysis will be performed based on the intention to treat concept.

All analyses concerning the competing risk model will be performed in R environment by using the library mstate and cprisk. All other analyses will be performed in SPSS version 26.0 (IBM Corp, Armonk, NY).

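### The chart permission sought at withdrawal (8.6) leaves out the primary event and is narrower than the continued follow-up promised in 10.2

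*Protocol*

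**What the plan says.** - **What is sought after withdrawal.** Section 8.6 stops the questionnaires for patients who withdraw after randomization and adds: "Patients are asked if it is allowed to consult their medical chart for treatment characteristics and survival length". No other section says what is collected from them.
- **What the first item means.** Table 1 uses the same label for a row on planning and dose: "GTV largest metastasis, PTV largest metastasis, total volume GTV of all metastases, and total volume PTV of all metastases", followed by maximum doses. ALE stands in a different row, under standard follow-up: "Follow-up MRI: adverse local event (either radionecrosis or local failure according to RANO), distant brain recurrences".
- **What is promised.** Section 10.2: "Care will be taken to minimize missing data and to continue to follow up those who withdraw from the study".
- **How these patients are analysed.** Section 8.5: "After the randomization, patients withdrawing for any reason will not be substituted by additional patients and these patients are analyzed by intention to treat".
- **Who else falls under the rule.** Section 8.4 covers patients who become incapacitated and can no longer be followed: "the same guidelines are followed as described for subjects who withdraw from the study for any reason", with a reference to 8.5 and 8.6.
- **Where the outcome comes from.** Section 8.1.1 makes ALE incidence at 2 years the primary endpoint. Section 8.3.9: "Tumor response evaluation as well as presence of distant brain recurrences are monitored every three months after SRT". Section 8.3 places this in routine care: "Procedures which are part of the standard medical treatment are summarized in paragraphs 8.3.1-8.3.9".
- **Consent.** Section 11.2 tells patients that their records may be reviewed for the trial. It does not say whether this continues after withdrawal. The consent form is a separate document and is not shown.

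**The concern.** A site that follows 8.6 to the letter asks for volumes, doses and survival, and does not ask for the primary outcome. It also does not ask for salvage treatment or distant brain recurrence, both secondary endpoints in 8.1.2. Unless an ALE was recorded before withdrawal, the patient's 2-year status can be unknown. The patient nevertheless stays in the intention-to-treat analysis, so the comparison has to rest on an assumption about that patient.

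The trial is open label, so the decision to withdraw can depend on the arm and can be related to how the patient is doing. An allowance in the sample size protects precision but does not protect against that bias. The loss is also avoidable, because many of the needed scans will be in the chart that 8.6 already asks to open. A later analysis plan can choose how to treat missing values, but it cannot recover data that nobody had permission to collect.

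**Working it through.** **1. The passages side by side.** Section 10.2 sets a general aim of continued follow-up and little missing data. Section 8.6 gives the operating rule, which lists two items. Survival is one of them, so some follow-up continues; the primary event is not among them. Section 8.5 is not contradicted in its wording, since it says only how withdrawn patients are analysed. In practice that analysis is weakened if their outcome is not collected.

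**2. The plan's own figure.** Inputs from section 4.4: 30% versus 10%, 59 per arm, two-sided alpha 0.05, pooled Z test with exact binomial probabilities. The rejection probability is the sum, over all outcome pairs (x, y) with |Z| ≥ 1.96, of Bin(x; n1, p1) × Bin(y; n2, p2). This gives power 0.8051 and, with 10% in both arms, actual alpha 0.0507. Both match the protocol.

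**3. Assumptions for the rest.** The protocol gives no withdrawal rate, no difference between arms and no ALE risk among those lost. All values of the following are therefore assumed:
- w = share withdrawing
- f = share of withdrawn patients' ALEs recorded before withdrawal
- q = ALE risk among those who withdraw

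There are 130/2 = 65 patients per arm. Deaths are ignored.

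**4. Power at 30% versus 10%, w = 10% in both arms.** When unrecorded ALEs count as event-free, the observed risk is p × (1 − w(1 − f)).

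| Handling | Observed risks | n per arm | Power |
|---|---|---|---|
| No loss | 0.30 vs 0.10 | 65 | 0.832 |
| Event-free, f = 0.5 | 0.285 vs 0.095 | 65 | 0.806 |
| Complete cases | 0.30 vs 0.10 | 58 | 0.797 |
| Event-free, f = 0 | 0.27 vs 0.09 | 65 | 0.779 |

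**5. Rejection rate with no true effect (30% in both arms).** With no loss it is 0.052. For the rows that leave out unknown status, the risk among those who stay is (0.30 − wq)/(1 − w), and the known-status risk is [(0.30 − wq) + wqf] / [(1 − w) + wqf].

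| Withdrawal | Handling | Observed risks | False difference (points) | Rejection rate |
|---|---|---|---|---|
| 5% vs 15% | Complete cases (62 vs 55), q = 0.3 | 0.30 vs 0.30 | 0 | 0.052 |
| 5% vs 10% | Event-free, f = 0.5, q = 0.3 | 0.2925 vs 0.285 | 0.75 | 0.053 |
| 5% vs 10% | Event-free, f = 0, q = 0.3 | 0.285 vs 0.27 | 1.5 | 0.056 |
| 5% vs 15% | Event-free, f = 0.5, q = 0.3 | 0.2925 vs 0.2775 | 1.5 | 0.056 |
| 5% vs 15% | Event-free, f = 0, q = 0.3 | 0.285 vs 0.255 | 3 | 0.069 |
| 5% vs 15% | Known status only (63 vs 59), f = 0.5, q = 0.8 | 0.2887 vs 0.2637 | 2.5 | 0.062 |
| 5% vs 15% | Known status only (62 vs 55), f = 0, q = 0.8 | 0.2737 vs 0.2118 | 6.2 | 0.124 |
| 5% vs 15% | All withdrawn counted as events, q = 0.3 | 0.335 vs 0.405 | 7 | 0.137 |

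Example for the 0.124 row: (0.30 − 0.05 × 0.8)/0.95 = 0.2737 and (0.30 − 0.15 × 0.8)/0.85 = 0.2118. For the last row: 0.95 × 0.30 + 0.05 = 0.335 and 0.85 × 0.30 + 0.15 = 0.405.

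**The case against.** The strongest points on the other side, and what stands of each:

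- **The two sections can both be carried out.** Section 10.2 is a best-effort sentence under the secondary parameters and names no data items, while 8.6 does follow survival. This stands in part: the conflict is one of scope. But the 10.2 sentence is worded for the whole study, and what falls outside the scope of 8.6 is the primary endpoint.
- **8.6 says what is asked and forbids nothing more, and its first item is never formally defined.** True. But Table 1 uses the same label for volumes and doses, and sites will act on the request as written.
- **The consent form may already permit wider use.** This stands. The permanent loss of data depends on a text that cannot be seen here. The wording of 8.6 would still need aligning with it.
- **Incapacitated patients will have few later scans.** This stands. For them the wording costs little, because most of the loss comes from the incapacity itself.
- **Nothing says that ALEs recorded earlier are discarded.** Correct, and their inclusion in the intention-to-treat analysis suggests that they are kept. Stating so is only a clarification.
- **The effect is small in plausible cases, and death will leave more 2-year outcomes unknown than withdrawal.** Section 9.2.2 expects survival of around 3 to 12 months, so withdrawal is probably not the main source of unknown status. The benign scenarios do stay at 0.052 to 0.056. This limits the weight of the point but gives no reason to leave an avoidable gap.

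**Conclusion.** The concern holds. Followed exactly, 8.6 does not seek the primary outcome of patients who withdraw, although routine care will often have recorded it, and this is narrower than what 10.2 undertakes. It is a stated data-collection rule, so it is not a detail that can be left to an analysis plan.

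The actual size is unknown. Under the assumptions above, power with 10% withdrawal in both arms is 0.779 to 0.806 against 0.805 planned, which is a minor loss. Bias matters more: it is absent if loss is uninformative and modest in the middle scenarios. The rejection rates of 0.124 and 0.137 require threefold differential withdrawal. The first also needs 80% ALE risk among those lost with none recorded, and the second needs every withdrawal coded as an event; the protocol proposes no such coding. The change should be made because it is cheap and protects the primary endpoint. Confidence is medium, given the unseen consent form.

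**What to change.** Reconcile 8.4, 8.6 and 10.2:

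- In 8.6 and the consent text, ask withdrawing patients for permission to take these items from the routine chart up to 2 years: ALE status with date, follow-up MRI results, salvage treatment, distant brain recurrence and survival.
- In 8.4, apply the same request to whatever scans were made in patients who become incapacitated.
- State that ALEs recorded before withdrawal are kept.
- State that patients who refuse are respected and remain missing.

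The cost is a few sentences in 8.4, 8.6 and the consent text. Patients already enrolled would be asked if and when they withdraw. The data come from routine care, so no visits or scans are added and the sample size does not change.

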### **8.7 Premature termination of the study**

The aim of the study is to investigate a different and possibly safer treatment method than the current standard of care. The study is based on the radiotherapy concept of fractionating the treatment. When the total dose of radiation is divided into several, smaller doses over a period of several days, there are fewer toxic effects on healthy cells. Therefore, the risk of adverse events in the experimental cohort is unlikely to be greater than in the standard cohort and premature termination of the study is not likely.

## 9. SAFETY REPORTING

### 9.1 Temporary halt for reasons of subject safety

In accordance to section 10, subsection 4, of the WMO, the sponsor will suspend the study if there is sufficient ground that continuation of the study will jeopardize subject health or safety. The sponsor will notify the accredited METC without undue delay of a temporary halt including the reason for such an action. The study will be suspended pending a further positive decision by the accredited METC. The investigator will take care that all subjects are kept informed.

### 9.2 AEs, SAEs and SUSARs

#### 9.2.1 Adverse events (AEs)

Adverse events are defined as any undesirable experience occurring to a subject during the study, whether or not considered related to the experimental intervention. All adverse events reported spontaneously by the subject or observed by the investigator or his staff will be recorded in the medical record of the patient.

#### 9.2.2 Serious adverse events (SAEs)

A serious adverse event is any untoward medical occurrence or effect that

- results in death;
- is life threatening (at the time of the event);
- requires hospitalization or prolongation of existing inpatients' hospitalization;
- results in persistent or significant disability or incapacity;
- is a congenital anomaly or birth defect; or
- any other important medical event that did not result in any of the outcomes listed above due to medical or surgical intervention but could have been based upon appropriate judgement by the investigator.

An elective hospital admission will not be considered as a serious adverse event.

The investigator shall report serious adverse events to [[contact]](mailto:[contact]) without undue delay after obtaining knowledge of the events, unless, for certain serious adverse events, the protocol provides that no immediate reporting is required.

Adverse experiences of a serious and unexpected nature, whether or not related to the cerebral radiotherapy, must be reported immediately. Adverse events that are

unexpected, should be reported if there is a possibility that it could be related to the administration of the radiotherapy.

The investigator will report all SAEs to the sponsor without undue delay after obtaining knowledge of the events, except for the following SAEs: epilepsy, deterioration of existing neurologic impairment after the radiotherapy, alopecia, fatigue, headache, and taste disorders.

The sponsor will report the unexpected SAEs through the web portal *ToetsingOnline* to the accredited METC that approved the protocol, within 7 days of first knowledge for SAEs that result in death or are life threatening followed by a period of maximum of 8 days to complete the initial preliminary report. All other unexpected SAEs will be reported within a period of maximum 15 days after the sponsor has first knowledge of the serious adverse events.

Patients with brain metastases generally have a poor life expectancy of around 3-12 months. Therefore, a significant proportion of patients is expected to die within the study duration of 1 year after SRT.

Expected SAEs are hospitalization or death by progression of both extracranial and intracranial cancer. Moreover, patients are treated with systemic therapy, and may be hospitalized or die because of complications of the systemic therapy, such as secondary infections. Furthermore, a proportion of patient will have severe neurologic impairment and epilepsy, because of intracranial cancer progression despite radiotherapy. These expected SAEs will be reported every half year in a line listing.

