As clinicians, we observe an increasing number of long term survivors over several years with brain metastases. Brain necrosis or radionecrosis is a long term side effect of SRT which occurs in +/-20% of patients and the incidence may increase up to +/-40% if SRT is combined with immunotherapy. Radionecrosis may cause neurologic symptoms, such as focal neurological deficits, neurocognitive dysfunction and seizures, which require treatment with steroids, bevacizumab, or sometimes even surgery. SRT is mostly delivered with an ablative high radiotherapy dose in a single fraction. In the first millimeters close to the brain metastasis, the healthy brain tissue receives a high dose as well.

In radiotherapy literature, it is known that more fractionated radiotherapy, e.g. hypofractionated radiotherapy (fSRT), may decrease side effects. fSRT means delivering the ablative dose in multiple fractions (f.e. 5 fractions) over several days instead of delivering the ablative dose within half an hour. Recent retrospective studies showed that risk difference of local failure and radionecrosis is almost 30% in larger tumors (>2.5 cm; constituting around

50% of metastases), while the incidence is equivalent in smaller metastases. To achieve a local control of more than 90% after one year, it is important to deliver a cumulative biologically effective dose (BED) of at least 50 Gy. 35 Gy in 5 fractions results in a BED of more than 50Gy. Another potential benefit of fSRT over SRT in one or three fractions is better induction of an abscopal effect. SRT in one or three fractions results in massive tumor necrosis. fSRT may result in more regulated cell death: apoptosis, with better antigen presentation of dying tumor cells. It is hypothesized that this may subsequently result in better activation of the immune cells against the cancer and better control of micrometastases outside the irradiation field. Several studies are ongoing in which SRT is combined with immunotherapy to increase systemic tumor control and thereby improve survival.

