### **9.5 Data Safety Monitoring Board (DSMB) / Safety Committee**

The establishment of a Data Safety Monitoring Board or Safety Committee is not deemed necessary for this study. The study aims to investigate a potentially safer treatment method than the current standard of care. It is unlikely that the risk of adverse events will be increased in the experimental cohort compared to the standard cohort. The only difference between the two cohorts is the fractionation schedule. The only difference is expected in the rate of local control and radionecrosis, which constitutes the primary study endpoint.

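### Section 9.2.2 gives serious worsening of an existing deficit, epilepsy or headache caused by radionecrosis no consistent reporting route to the sponsor

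*Protocol*

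**What the plan says.** Three rules in Protocol section 9.2.2 bear on the same events.

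- **Exemption.** Investigators report all SAEs to the sponsor promptly, with the exception of epilepsy and "deterioration of existing neurologic impairment after the radiotherapy, alopecia, fatigue, headache, and taste disorders". Nothing in this list depends on the cause of the event.
- **Serious unexpected events.** A few lines earlier: "Adverse experiences of a serious and unexpected nature, whether or not related to the cerebral radiotherapy, must be reported immediately".
- **Half-yearly listing.** The expected SAEs are hospitalization or death from cancer progression, complications of systemic therapy, and the neurological item: "a proportion of patient will have severe neurologic impairment and epilepsy, because of intracranial cancer progression despite radiotherapy". Then: "These expected SAEs will be reported every half year in a line listing".

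Radionecrosis appears neither among the exemptions nor among the expected SAEs. Section 1 describes its effects: "Radionecrosis may cause neurologic symptoms, such as focal neurological deficits, neurocognitive dysfunction and seizures". Section 8.1.1 makes it one of the two components of the primary endpoint.

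On oversight, section 9.5 states: "The establishment of a Data Safety Monitoring Board or Safety Committee is not deemed necessary for this study". The annual safety report (9.3) is marked not applicable. The interim analysis section (10.4) only points to section 8.7, which describes none.

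**The concern.** The exemption is defined by type of event, while the neurological part of the listing is defined by cause. Events of an exempt type with a cause other than progression can fall between the two. Radionecrosis is the obvious such cause, and it is the main treatment harm that the trial is meant to reduce.

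What is at stake is safety oversight during the trial, not the primary comparison. Section 9.1 obliges the sponsor to suspend the study if continuing would endanger subjects. To judge that, the sponsor needs serious, possibly treatment-related events to reach it. Section 3 places the statistical analysis in March 2027, five years after the planned start of data collection in March 2022, and the protocol schedules no earlier review of the outcome data.

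**Working it through.** No arithmetic decides this point. The check follows each kind of neurological SAE through the three rules of section 9.2.2.

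| Serious event | On exemption list? | In half-yearly listing as worded? | Caught by the rule on serious unexpected events? |
|---|---|---|---|
| Existing deficit worsens, due to progression | Yes | Yes, if severe | No, it is listed as expected |
| Existing deficit worsens, due to radionecrosis | Yes | No, wrong cause | Yes, if events not listed as expected count as unexpected |
| Existing deficit worsens, cause undetermined | Yes | No, cause condition not met | Unclear |
| Epilepsy, due to progression | Yes | Yes | No |
| Epilepsy, due to radionecrosis | Yes | No | Yes, on the same reading |
| Headache, due to radionecrosis | Yes | No | Yes, on the same reading |
| New deficit, due to radionecrosis | No | No | Yes, and reportable promptly in any case |
| SAE recorded as radionecrosis | No | No | Yes, and reportable promptly in any case |

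The table shows three things.

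1. **Contradiction.** In rows 2, 5 and 6 one sentence waives prompt reporting and another requires immediate reporting. The section does not say which prevails, so two sites could handle the same event differently and both claim to follow the protocol.
2. **Gap.** If the exemption prevails, rows 2, 5 and 6 have no stated route, because the listing does not cover them. Row 3 is in the same position until a cause is assigned.
3. **Listing without a stated input.** Rows 1 and 4 belong in the listing, yet they are of exempt types and no later report from investigator to sponsor is described. Section 9.2.1 requires adverse events to be recorded in the patient's medical record, which does not by itself bring them to the sponsor.

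Section 1 names deficits and seizures as effects of radionecrosis. It does not name headache. Row 6 assumes that radionecrosis can also present as a serious headache.

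**Other channels.** The annual progress report to the METC (12.4) includes SAEs and serious adverse reactions. It is the sponsor's report and can hold only what the sponsor has received. Table 1 schedules symptomatic radionecrosis and toxicity every three months, although section 8.3.10 speaks of evaluating symptomatic radionecrosis two years after SRT. Either way this is data collection, with no review attached before the analysis.

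**The case against.** The strongest reply is that the exemption concerns timing only. Section 9.2.2 opens by allowing that certain SAEs need no immediate reporting, and the exception list is attached to the duty to report promptly. This is a fair reading, and it means the protocol does not plainly tell investigators never to report these events. It does not close the gap, because no later deadline, form or listing is given for exempted events that are not due to progression.

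A second reply is that the rule on serious unexpected events captures radionecrosis-related deterioration, since radionecrosis is not listed as expected. If that rule prevails, the events are reported. The protocol does not say that it prevails, and a site may equally take the exemption list as showing that these events are expected.

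Third, there are other sources of information. The trial is open label, the sponsor arranges monitoring once or twice a year (12.2), the coordinating and principal investigators can view the coded data (12.1), and the METC receives a yearly progress report. These stand as facts, and SAE reporting is not the only way the sponsor could learn of such an event. None of them is a defined safety review or a rule that brings the exempted events forward.

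A reader might infer more than the text supports, in three ways:

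- **That all serious neurological harm from radionecrosis goes unreported.** It does not. New deficits and SAEs recorded under the diagnosis of radionecrosis are not exempt.
- **That the protocol requires no reports at all for patients with an existing deficit.** The rule on serious unexpected events prevents that conclusion.
- **That the affected number follows from the incidence in section 1.** Applying about 20% and about 40% to 130 patients gives 0.20 × 130 = 26 and 0.40 × 130 = 52. This counts radionecrosis of any severity, and the upper rate is stated only for SRT combined with immunotherapy. It does not measure the gap.

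**Conclusion.** The inconsistency is real and limited. It concerns serious worsening of an existing neurologic impairment, epilepsy and headache when radionecrosis is the cause, or when no cause has been assigned. For the radionecrosis-caused events, section 9.2.2 contradicts itself on prompt reporting and leaves them out of the half-yearly listing. With no DSMB, annual safety report or planned interim analysis, the one remaining scheduled report is the yearly progress report, and no rule feeds these events to it.

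The number of patients affected cannot be derived. It requires radionecrosis, seriousness, presentation as an exempt event type, and recording as that type and not as radionecrosis. The protocol gives a rate only for the first.

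The primary endpoint is assessed on scheduled MRI and is not affected. The point still warrants an amendment, because a rule followed as written can keep serious, possibly treatment-related events from the sponsor.

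The conclusion assumes that the listing is confined to the SAEs described just before it, and that no separate safety document supplies the missing route.

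**What to change.** Reconcile the rules in section 9.2.2:

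1. State that the exemption concerns immediate reporting only, and that every exempted SAE type is still reported to the sponsor on the SAE form.
2. Put all exempted SAE types in the half-yearly line listing whatever the cause (progression, radionecrosis or undetermined). Remove progression as a condition for listing the neurological events.
3. Show cohort and investigator-assigned cause for each listed event.
4. State which rule prevails when an exempted event is also serious and unexpected.

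This is a short amendment to one section, plus two columns in a listing that is already planned. Sites will complete some additional SAE forms. Items 1 to 3 add no expedited reporting. Whether item 4 does depends on which rule the sponsor lets prevail.
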